If an unacceptable AE develops at any time during titration, dosing should initially be suspended or amended, at the Investigator's discretion, as appropriate, until the event has resolved or is well tolerated. During the maintenance period, Investigators may decrease the dose if a patient experiences intolerance, or increase the dose if required for better seizure control, until the optimal dose is found. The Investigator may schedule additional clinic visits during the maintenance period to facilitate dose adjustments, e.g., when increasing doses above 20 mg/kg/day. Patients whose dose has been decreased can have their dose increased again provided there is adequate tolerance. Dose increases above 20 mg/kg/day are recommended to be done slowly, with maximum increments of 2.5 mg/kg every 5–7 days. The maximum dose patients can receive will be 30 mg/kg/day.

For patients who do not immediately continue to use GWP42003-P following the 'End of Treatment' visit, IMP will be down-titrated at home (10% per day for 10 days). Additional IMP will be dispensed, if required. Patients who withdraw early should also begin the taper period following the Withdrawal visit (unless continued dosing is not possible due to an AE). The IVRS will generate the patient's daily IMP dosing volumes for the 10-day taper period, during which time IVRS and diary information will continue to be recorded.

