If the severity of an AE fluctuates day-to-day, for example, a headache or constipation, the change in severity should not be recorded each time, instead only the worst observed severity should be recorded with AE start and stop dates relating to the overall event duration regardless of severity.

A severe AE is not the same as a SAE. For example, a patient may have severe vomiting but the event does not result in any of the SAE criteria above. Therefore it should not be classed as serious.

E) Causality

See [Section 12.5](#) above.

F) Action Taken with Study Medication

This question refers to the action taken with the IMP due to an AE. The action with the IMP must be classed as:

- None.
- Dose reduced temporarily.
- Dose reduced.
- Study medication interrupted.
- Study medication stopped.

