13.6 Endpoints and Statistical Methods

13.6.1 Evaluable Period

All data collected during this study will be summarized across time, using appropriate descriptive statistical methods. Where baseline data are available from the Core Studies (such as seizure frequencies, quality of life assessments, Vineland-II, other measures of safety [such as vital signs, clinical laboratory samples]), changes from pre-randomization baseline of the Core Study will also be presented. Treatment compliance and exposure to treatment will also be summarized.

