4.5.2 Adverse Events

All reported AEs will be classified by system organ class (SOC), preferred term and lower level term using Version 17.1 of MedDRA.

Summaries will be presented by SOC and preferred term.

A treatment emergent AE (TEAE) is defined as an AE with a start date on or after the first dose of IMP within this OLE study. If an AE has a partial start date and it is unclear from the partial date (or the stop date) whether the AE started prior to or post first dose of IMP then the AE will be considered treatment emergent. If the start date of the AE is the same as the date of first dose of IMP and the plausible relationship to study medication is marked on the CRF as "Prior to study medication" then the AE will not be considered treatment emergent.

An AE will be considered treatment-related if the plausibility relationship to study medication is recorded on the CRF as 'yes'. If the data on plausibility relationship to study medication is missing then the AE will be considered treatment-related.

An AE will be considered leading to permanent discontinuation of study medication if the action taken with study medication is recorded on the CRF as 'study medication stopped'.

An AE will be considered fatal if the outcome is recorded on the CRF as 'patient died'.

The following summaries will be generated:

- Overall summary of AEs, including number of patients reporting each of; TEAEs, treatment related TEAEs, TEAEs leading to withdrawal, treatment related TEAEs leading to withdrawal, serious TEAEs, treatment related serious TEAEs.
- Summary of TEAEs.
- Summary of treatment-related TEAEs.
- Summary of TEAEs by maximal severity.
- Summary of TEAEs by sex.
- Summary of serious TEAEs.
- Summary of treatment-related serious TEAEs.
- Summary of TEAEs leading to permanent discontinuation of study medication.

- Summary of treatment-related TEAEs leading to permanent discontinuation of study medication.
- Summary of fatal TEAEs.
- Summary of TEAEs by time of first onset of AE.
- Summary of TEAEs by time to AE resolution.
- List of patients experiencing TEAEs by SOC and preferred term.

For the summary of TEAEs by maximal severity, for each patient, the worst severity recorded by preferred term, SOC and overall will be used for summary purposes. If severity is missing, the worst case (severe) will be assumed.

For the summary of TEAEs by time of first onset of AE, data will be summarized under the following categories:

- Weeks 1 to 2 (Day 1 to 14).

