4.5.8.13 Exposure to Study Medication

Patients are required to take IMP twice daily (morning and evening). The first OLE dose will be taken in the clinic on Visit 1 (Day 1). The date of final dose in the study will be recorded on the CRF. The date of final dose, for patients who enter the taper period, will be recorded on the CRF at the end of taper visit.

The total number of dosing days in the study will be calculated as:

$$(\text{Date of last dose in the treatment phase} - \text{Date of Day 1}) + 1$$

The date of last dose in the treatment phase will be obtained from the CRF at the end of treatment visit.

The total number of dosing days in the study will be summarized for all patients, and patients who completed the treatment phase. The modal dose will be calculated for each patient over the same periods associated with IVRS calls for seizure reporting and will subsequently be summarized. Furthermore, a categorical summary of patients whose largest dose was 20 mg/kg/day or less, patients whose largest dose was over 20 mg/kg/day and less than 30 mg/kg/day, and patients whose largest dose was 30 mg/kg/day or more during the OLE study will be presented.

The above summaries will be repeated for the following subgroups:

- Excluding data for patients from study GWEP1332 Part A
- Patients taking clobazam
- Patients not taking clobazam
- Core study actual treatment: GWP42003-P
- Core study actual treatment: Placebo
- Patients taking clobazam; core study actual treatment: GWP42003-P
- Patients not taking clobazam; core study actual treatment: GWP42003-P
- Patients taking clobazam; core study actual treatment: Placebo
- Patients not taking clobazam; core study actual treatment: Placebo

The modal dose for each patient will be calculated across their entire period of exposure, and the number of patients and patient-years exposure will be summarized in the following groups:

- $\leq 20\text{mg/kg/day}$
- $20 - < 25\text{mg/kg/day}$
- $\geq 25\text{mg/kg/day}$

For each group, the total number of patient-years of exposure will be calculated as the sum of the total number of dosing days for each patient divided by 365.25. For the calculation of modal dose, patients will be assumed to be taking 20 mg/kg/day unless a dose adjustment is recorded.

Any missed doses during treatment should be recorded on the 'IMP Missed Doses Log' CRF page.

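### No SAP table shows how many patients had a dose reduced or interrupted because of an adverse event, and suspended days are counted as dosing days

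*SAP*

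**What the plan says.** **How intolerance is handled.** Protocol 8.1.2 says that for an unacceptable event in titration "dosing should initially be suspended or amended, at the Investigator's discretion, as appropriate, until the event has resolved or is well tolerated". In maintenance it lets the investigator lower the dose for intolerance. Protocol 12.6 (item F) requires one of five actions to be recorded for each AE: none, two kinds of reduction (including "Dose reduced temporarily"), "Study medication interrupted", and stopped.

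**What the SAP does with that record.** SAP 4.5.2 defines one category from it: "An AE will be considered leading to permanent discontinuation of study medication if the action taken with study medication is recorded on the CRF as" stopped. Its list of outputs has "Summary of TEAEs leading to permanent discontinuation of study medication" (Table 12.3) and a treatment-related version (Table 12.4), and the overall summary (Table 11.1) has rows for withdrawal. The table list in SAP Appendix 5 has nothing for reduction or interruption.

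**Exposure.** SAP 4.5.8.13 states: "The total number of dosing days in the study will be calculated as" the last treatment-phase dose date minus Day 1, plus 1. Patient-years are the sum of those days divided by 365.25. Missed doses go on a CRF log, but no derivation uses it. Dose is summarized by largest dose, by modal dose per period, and by modal dose over the whole stay.

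**Compliance.** Protocol 13.6.1 says: "Treatment compliance and exposure to treatment will also be summarized". The SAP has exposure tables and an IMP accountability listing (Listing 10.3), but no compliance table. SAP 4.7, which lists what was dropped from the protocol, does not mention it.

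**The concern.** In a flexible-dose extension, permanent stopping is usually the last sign of intolerance. A patient whose dose is cut or suspended because of an event, and who then carries on, is managed as the protocol intends. How often that happens, and for which events, is a central tolerability result. The data are collected for every event, but the planned tables report only the final step.

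The exposure rule has a related fault. A figure called dosing days that includes days without drug is too large, and it is too large in exactly the patients whose dosing was interrupted. The compliance summary, which could have shown those gaps, is missing without explanation.

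**Working it through.** The plan states no figure on this point, so there is nothing to reproduce. The check applies the SAP's own rules.

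**1. Action-taken categories against SAP tables**

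| Action recorded (protocol 12.6) | SAP table of TEAEs |
|---|---|
| None | no separate table |
| Temporary reduction | no separate table |
| Reduction | no separate table |
| Interruption | no separate table |
| Stopped | Tables 12.3, 12.4 |

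Events in every row are still counted in the general TEAE tables (11.1 to 11.7).

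**2. Can the dose summaries fill the gap?**

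- *Largest dose.* The lowest class holds everyone who never exceeded 20 mg/kg/day. A patient cut from 20 to 5 is classed with one who stayed at 20.
- *Modal dose over the whole stay.* The lowest class again holds every dose below 20, so a reduction cannot be seen.
- *Modal dose by period.* The periods are those tied to IVRS seizure reporting, which could mean 12-week periods or weekly calls. In an 84-day period that starts at 20, 41 days at one lower dose leave 43 days at 20, so the mode stays at 20. At 42 days there is a tie. From 43 days the mode moves. In a 7-day period, 4 days suffice.
- *Default.* The modal dose is taken as 20 mg/kg/day if no adjustment was recorded. The SAP does not say whether an entry in the missed-dose log, or an interruption recorded against an AE, counts as an adjustment.
- *Cause.* The protocol's target is a range, 10–20 mg/kg/day, so a modal dose below 20 does not by itself indicate intolerance. Only the action-taken field links the change to an event.

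**3. Dosing days for one patient**

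Net days = SAP days − gap. Overstatement = gap ÷ net days. Gap lengths are assumed.

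| SAP dosing days | Gap (days) | Net days | Overstatement |
|---|---|---|---|
| 168 (24 weeks) | 28 | 140 | 28/140 = 20% |
| 336 (48 weeks) | 7 | 329 | 7/329 = 2.1% |
| 336 | 14 | 322 | 14/322 = 4.3% |
| 336 | 28 | 308 | 28/308 = 9.1% |
| 728 (104 weeks) | 28 | 700 | 28/700 = 4.0% |

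**4. Patient-years for the study**

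The planned enrolment is 680 (protocol 4.3). Assume each patient stays 730 days and 10–30% have one gap of 7–28 days.

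- By the SAP rule: 680 × 730 ÷ 365.25 = 1359.1 patient-years.
- Low end: 680 × 0.10 × 7 ÷ 365.25 = 1.3 off drug; 1.3 ÷ (1359.1 − 1.3) = 0.1%.
- High end: 680 × 0.30 × 28 ÷ 365.25 = 15.6 off drug; 15.6 ÷ (1359.1 − 15.6) = 1.2%.

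Shorter stays would raise these percentages.

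**The case against.** The strongest reply has five parts.

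- **All TEAEs are tabulated**, by system organ class and preferred term, relatedness, "Summary of TEAEs by maximal severity", sex, onset and resolution, with separate tables for serious and fatal events. This stands. A reader might infer that events managed by a lower dose drop out of the results. They do not; what is missing is the breakdown by action taken.
- **Modal dose by period is summarized**, and repeated in subgroups, from recorded adjustments. Exposure by time is also listed (Listing 10.2). This stands for sustained, recorded reductions. It does not cover short ones, and it does not say why the dose changed.
- **The protocol's own AE list (13.6.2.1) names only permanent cessation.** This stands too. On the AE tables the SAP follows the protocol, and the gap is common to both. The reply does not reach the compliance summary, which the protocol promises.
- **Patient-years feed no AE rate.** A reader might infer that inflated exposure dilutes the safety rates. The SAP plans no exposure-adjusted incidence. Its AE summaries count patients, and patient-years appear only in the modal-dose grouping (Table 10.6). No AE percentage would change.
- **The CRF is not available here.** The documents show action categories but no start and stop dates for interruptions, and the layout of the missed-dose log is unknown. Exact netting of off-drug days may not be possible, and the fix has to allow for that.

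**Conclusion.** The point holds in a limited form. No planned table gives the number of patients with an AE-driven dose reduction or interruption, or the events responsible, although the field is collected and tolerability is part of the primary objective. The size of this gap cannot be stated, because the documents give no rates of dose change.

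The dosing-days rule gives a number that is too large. For one patient with 28 days off drug, the excess is 4% over 104 weeks and 20% over 24 weeks. At study level it is about 0.1–1.2% under the assumed gap frequency, gap length and 730-day stay. That is small and leaves the AE percentages untouched, so the missing tolerability tables matter more. The compliance summary is an undeclared omission from the protocol's plan.

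A reader might go further and conclude that the tolerability result is built to look good. The documents do not support that: the severity, relatedness and seriousness of all TEAEs are reported, and permanent stopping is the only action-based summary the protocol itself asks for.

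**What to change.** - **SAP 4.5.2 and Appendix 5.** From the action-taken field, add one table of TEAEs leading to dose reduction (temporary or lasting) and one of TEAEs leading to interruption. Add a row to Table 11.1 for patients with any AE-driven dose change.
- **SAP 4.5.8.13.** Report dosing days and patient-years net of off-drug days, as far as the missed-dose log and recorded interruptions allow. If they do not, keep the current figure and relabel it as time from first to last dose.
- **Compliance.** Add the summary promised in protocol 13.6.1.

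The AE tables need no new data. The cost is SAP wording, a few extra tables, and a tolerability picture that will look somewhat less favourable. No dosing rule changes.

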4 EXPERIMENTAL PLAN

4.1 Study Design

This is a multi-center, OLE study for patients with DS or LGS who have completed the double-blind, placebo-controlled, clinical studies of GWP42003-P (Core Studies). The study consists of a titration period and a maintenance period, followed by a 10-day taper period.

Titration Period: All patients will titrate up to 10–20 mg/kg/day GWP42003-P using a recommended titration schedule (see [APPENDIX 4](#)). It is advised that the Investigator considers monitoring hepatic function (alanine aminotransferase [ALT], aspartate aminotransferase [AST], total bilirubin [TBL] and international normalized ratio [INR] levels) during the titration period for patients taking concomitant AEDs that are known to be associated with hepatic injury or failure. To minimize any elevations in hepatic function markers the titration period can be extended and the dosage of a concomitant AED and/or GWP42003-P may be adjusted at the discretion of the Investigator. If there is intolerance during titration, the patient may be maintained on a dose below 10–20 mg/kg/day. A titration rate faster than recommended may be considered if there is an increase in seizures, following consultation with the GW medical monitor.

Maintenance Period: Patients will continue dosing at 10–20 mg/kg/day. However, Investigators may decrease the dose if the patient experiences intolerance, or increase the dose if required for better seizure control, until the optimal dose is found. The Investigator may schedule additional clinic visits to facilitate dose adjustments e.g., when increasing doses above 20 mg/kg/day. Patients whose dose has been decreased can have their dose increased again provided there is adequate tolerance. The maximum dose patients can receive will be 30 mg/kg/day (51 mg/kg/day is the maximum dose safely used in the USA EAP to date with a mean dose of 24 mg/kg/day [$n = 59$]). Dose increases above 20 mg/kg/day are recommended to be done slowly, with maximum increments of 2.5 mg/kg every 5–7 days. If seizure freedom is achieved with use of GWP42003-P during the study, the Investigator can consider reducing the dose of concomitant AEDs after consultation with the GW medical monitor.

Study Completion: The maximum duration of this OLE study will be 4 years (208 weeks after Visit 1).

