3.1.3 Study Completion and Taper Period

If market authorization is granted for GWP42003-P (in DS or LGS) or after a maximum period of time receiving treatment, depending on the country in which the patient enrolls, (whichever occurs first), the patient will complete the study. Patients who do not immediately continue to use GWP42003-P will then commence a taper period (down-titrating 10% per day for 10 days) and complete an 'End of Taper Period' visit followed by a Follow-up visit (can be by telephone) four weeks later. If a patient opts not to continue with GWP42003-P treatment, they will commence the 10-day taper period and complete the 'End of Taper Period' visit and the Follow-up visit. If supported by the safety data, the Sponsor will look to extend the duration of this study.

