4. STATISTICAL METHODS

4.1 General Considerations

All tables will be presented by indication (where appropriate), including an overall count, as follows:

Dravet Syndrome (N=XX)	Lennox-Gastaut Syndrome (N=XX)	Overall (N=XX)
------------------------	--------------------------------	----------------

In all tables, listings and figures, the study visits will be referred to and labelled as per [Table 2](#)

Table 2 Study Visits

Actual Visit	Visit Label
Visit 1: Day 1	Day 1
Visit 2: Day 15	Day 15
Visit 3: Day 29	Day 29
Visit 4: Day 85	Day 85
Visit 5: Month 6 or Week 24	Week 24
Visit 6: Month 9 or Week 38	Week 38
Visit 7: Week 48 or End of Treatment (only patients who completed at 1 year)*	Week 48
Visit 8: Week 76	Week 76
End of Treatment (only patients who completed on or after Day 400)*	End of Treatment

End of Treatment (withdrawn patients only)	End of Treatment
End of Taper	End of Taper
Post-Taper Safety Call	Post-Taper Safety Call
Safety Follow-Up	Safety Follow-Up

* For some patients, the end of treatment visit occurs after one year in the OLE, whereas for other patients the end of treatment visit occurs after two or more years in the OLE.

Unless stated otherwise, continuous variables will be summarized showing the number of non-missing values (n), mean, standard deviation, median, minimum and maximum and categorical variables will be summarized showing the number and percentage of patients falling in each category. For continuous summaries of seizure frequency, the lower and upper quartiles will also be presented.

Minimum and maximum values will be presented to the same decimal precision as the raw data. Mean and median will be presented to one more decimal place than the raw data, and standard deviation to 2 more decimal places than the raw data. Percentages will be presented to one decimal place.

For patients who enter the OLE on the same day as the core study end of treatment or end of taper visit, the CRF for this study did not require some data to be entered for a second time. Hence, for visit based endpoints, if a patient does not have data entered in this study at Visit 1, then data from the end of treatment or end of taper visit in the core study will be used, provided that the date of collection is on Day 1 of the OLE.

Unless otherwise stated, all summaries will be presented by indication.

All analyses and summaries will be produced using SAS Version 9.4.

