- Weeks 3 to 6 (Day 15 to 42).
- Weeks 7 to 10 (Day 43 to 70).
- Weeks 11 to 14 (Day 71 to 98).
- >14 weeks (> Day 98).

The time to first onset of AE will be calculated for TEAEs as:

$$\text{Start date of AE} - \text{Date of first dose of OLE IMP} + 1$$

If patients have multiple occurrences of an AE then the AE will be counted once for the first occurrence only. Percentages will be based on the number of patients in the safety analysis set who have a visit or follow-up call within each time period above.

For the summary of TEAEs by time to AE resolution, data will be summarized under the following categories:

- 1 week (≤ 7 days).
- 2 weeks (8 to 14 days).
- 3 weeks (15 to 21 days).
- 4 weeks (22 to 28 days).
- >4 weeks (>28 days).
- Ongoing (for AEs not resolved).

The time to AE resolution will be calculated for TEAEs as:

$$\text{Stop date of AE} - \text{Start date of AE} + 1$$

If patients have multiple occurrences of an AE then the AE will be counted once for the occurrence with the longest time to AE resolution. However, if any of the AEs are not resolved, then the AE will be counted once within the 'Ongoing' category.

For time of first onset of AE and time to AE resolution, partial or missing dates will be handled according to Section 4.1.2.2. If an AE has a partial start date and it is unclear from the partial date (or the stop date) whether the AE started prior to or post first dose of IMP then the start date will be imputed as the date of first dose of IMP in the OLE (Day 1). The start and stop day of the AE relative to the first dose of IMP (as recorded on the CRF) will be calculated as per Section 4.1.3. For partial dates, if it is clear from the partial date that

the start/stop day was prior to the first dose of IMP, then 'pre' will be listed, similarly if it is clear that the event was post the first dose of IMP then 'post' will be listed as the start/stop day as appropriate.

All AEs will be listed. Listings will include the start and stop day of the AE, a flag for treatment emergence, and limited demographic information about the patient (age, sex, race and weight at screening). A separate listing will be provided for pre-treatment AEs, serious AEs and events of special interest (see [Appendix 1](#)).

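### The AE tables pool every first onset after Day 98 in one open bin and use no person-time, so they cannot show when AEs first arise during long-term treatment

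*SAP*

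**What the plan says.** SAP 4.5.2 groups TEAEs by day of first onset after the first OLE dose: Days 1-14, 15-42, 43-70, 71-98, and then ">14 weeks (> Day 98", with no upper limit. An AE counts once per patient, at its first occurrence. The denominator is a head count: "Percentages will be based on the number of patients in the safety analysis set who have a visit or follow-up call within each time period".

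Appendix 5 lists 13 AE tables (11.1-11.8 and 12.1-12.5). Only Table 11.6 runs on time since first OLE dose. Table 11.7 is by duration of the event. The others cover the whole OLE, by system organ class and preferred term, severity, sex, relatedness, seriousness, discontinuation or death.

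Follow-up is long and unequal. Protocol 4.1 states: "The maximum duration of this OLE study will be 4 years (208 weeks after Visit 1". SAP Table 2 has a row "Visit 7: Week 48 or End of Treatment (only patients who completed at 1 year", with the footnote "For some patients, the end of treatment visit occurs after one year in the OLE, whereas for other patients the end of treatment visit" comes after two or more years. SAP 3.1.3 has patients finishing "after a maximum period of time receiving treatment, depending on the country in which the patient enrolls", if authorization does not come first.

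Person-time appears only under exposure. SAP 4.5.8.13 says "The total number of dosing days in the study will be summarized for all patients, and patients who completed the treatment phase" (Table 10.1) and, by modal dose, "For each group, the total number of patient-years of exposure will be calculated as the sum of the total number of dosing days", divided by 365.25 (Table 10.6). Neither table carries AE counts.

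**The concern.** The four resolved bins span 14 weeks. According to SAP Table 1, that is also the length of the treatment period in four of the five core study parts. The AE tables therefore give detail for a span already studied under placebo control, and collapse the span that only this extension adds.

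Two things follow. First, a patient last contacted on Day 99 adds as much to the open bin's denominator as one followed for years, so the percentage rises with length of follow-up even when risk does not change. Second, the entry is the same whether first onsets cluster soon after Week 14, spread evenly, or come late. For a study meant to characterize long-term safety, that is a question a reader will bring to the AE tables.

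**Working it through.** The plan states no figure to reproduce here. The bin edges agree with their week labels (2, 6, 10 and 14 weeks = Days 14, 42, 70 and 98).

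**Share of the course in the open bin**, (T - 14)/T:
- 48 weeks: 238/336 days = 70.8%
- 104 weeks: 630/728 days = 86.5%
- 208 weeks (maximum): 1358/1456 days = 93.3%

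All AE rates below are assumptions.

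**Effect of follow-up.** Let p = 3% have the AE by Week 14 at a constant hazard.
- h = -ln(0.97)/14 = 0.002176 per week, or 11.4 per 100 patient-years.
- Open bin = 0.97 x (1 - exp(-h(T - 14))).
- T = 48: 0.97 x (1 - exp(-34h)) = 6.9%.
- T = 104: 0.97 x (1 - exp(-90h)) = 17.2%.

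The risk per unit time is identical in both rows.

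**Effect of shape.** Everyone is followed to Week 104, with multipliers on h over Weeks 15-59 and Weeks 60-104 (45 weeks each):
- falling (1.5, 0.5): 17.0 then 5.7 per 100 patient-years
- flat (1, 1): 11.4 throughout
- rising (0.5, 1.5): 5.7 then 17.0

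The cumulative hazard is 90h in each case, so all three show 17.2%. First events in Weeks 73-96 (Day 505-672) are 0.97 x [exp(-H(72)) - exp(-H(96))], where H is the hazard accumulated since Week 14:

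| Shape | H(72) | H(96) | First events, Weeks 73-96 |
|---|---|---|---|
| Falling | 74h | 86h | 2.1% |
| Flat | 58h | 82h | 4.4% |
| Rising | 42h | 78h | 6.7% |

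**What can still be recovered.** Table 11.6 counts first occurrences, so its first four bins give the share p already affected by Day 98. With equal follow-up to Week 104, the average later hazard is -ln(1 - open/(1 - p))/90, to be compared with -ln(1 - p)/14. When the true later rate is half, equal to or double the earlier one, this returns ratios of exactly 0.5, 1.0 and 2.0 at p = 3%, 10% and 30%.

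With unequal follow-up it is only rough. Take p = 30%, constant hazard h = -ln(0.7)/14 = 0.02548 per week, half the patients followed to Week 48 and half to Week 104 (mean 62 weeks after Week 14):
- open/(1 - p) = [(1 - exp(-34h)) + (1 - exp(-90h))]/2 = (0.579 + 0.899)/2 = 0.739
- -ln(1 - 0.739)/62 = 0.0217, a ratio of 0.85 where the truth is 1.0

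**The case against.** The study is single-arm and descriptive, with no hypothesis testing. Protocol 13.6.2.1 lists the AE summaries and none is by onset time, so Table 11.6 already goes further than that list. Every AE's start day is listed, with a separate listing of serious AEs. Later windows would describe selected patients with changing doses and concomitant AEDs. All of this stands. It makes the point an improvement to the planned summaries, not an error or a breach of the protocol. It does not let a table entry distinguish early from late onset, and listings are not a summary for a study of about 680 patients.

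A reader might infer three stronger things that the documents do not support.
- **That no usable rate after Day 98 can be had for common AEs.** Dividing the open-bin percentage by elapsed time does mislead for common AEs, but only because patients already affected stay in the denominator. Table 11.6 supplies that correction, as shown above.
- **That the number still under observation is unknown.** Withdrawals by period do not count one-year completers. However, n by period comes with the modal-dose and seizure summaries (the latter without GWEP1332 Part A), and n by visit with the laboratory, vital-sign and ECG tables.
- **That 93% is the typical share of follow-up in the open bin.** It applies only at the 208-week maximum. Protocol 4.1 lets patients finish from about two years once the product is commercially available, and SAP Table 2 has no scheduled visit label after Week 76 before End of Treatment.

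Other safety outputs are resolved over time (C-SSRS and epilepsy hospitalizations by visit, status epilepticus by 12-week period), but they cover their own measures, not AE onset.

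**Conclusion.** The gap is real and limited. Table 11.6 is the only AE table on time since first OLE dose. Its last bin takes 71% of a 48-week course and 87% of a 104-week course, over a head count of patients with unequal follow-up, and no AE table uses person-time. The open-bin percentage therefore mixes risk with observation time: 6.9% against 17.2% at one constant hazard. It cannot show whether first onsets come early, evenly or late after Week 14: 17.2% for all three shapes, against 2.1%, 4.4% and 6.7% in Weeks 73-96.

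The shares follow from the documents. The percentages rest on an assumed 3% by Week 14, on piecewise-constant hazards and on complete follow-up to the stated week. An average later rate, the numbers remaining and individual start days can all be obtained from planned outputs; the shape of AE onset after Day 98 is not summarized in any of them. It should be fixed because the primary objective is long-term safety.

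**What to change.** In SAP 4.5.2 and Appendix 5:

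1. Keep the bins to Day 98. Split the rest into Day 99-168 and then 24-week windows on the 4.5.9 grid (Day 169-336, 337-504 and so on), pooling late windows where few patients remain. That is 5 windows to Week 104, or 9 to Week 208. Apply this to any TEAE, serious TEAEs, system organ classes, and preferred terms above a frequency cut stated in the SAP.
2. In each window, report first events per 100 patient-years at risk, with patients leaving the risk set at their first event. In the illustration, Weeks 73-96 would then read 5.7, 11.4 or 17.0.
3. Add exposure-adjusted rates to the TEAE, serious TEAE and discontinuation tables, with person-time running to the last AE contact. The 4.5.8.13 patient-years stop at the last treatment-phase dose, whereas the TEAE definition has no end date and Protocol 12.6 collects AEs through the Follow-up visit. Using those patient-years unchanged would count taper and follow-up events without their time, about 10 + 28 = 38 days per patient who tapers.

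This is a cheap improvement: SAP wording and programming on periods and start days already defined, with no new data. The costs are longer output, at-risk time to program per term and window, and small denominators in late windows. The 24-week grouping, the pooling and the frequency cut limit these.
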